# Amendment to recruitment protocol

We will also recruit UCLA patients. The recruitment methods will differ from those above because they involve patients from a different institution with their own IRB and Compliance Office (Privacy). The recruitment will begin with a query of the UCLA Data Warehouse to identify patients on target medications. Second, potentially eligible patients will be sent a UCLA recruitment letter and opt-in/out form. Patients who do not opt-out will be contacted following a UCLA IRB approved telephone screening protocol. UCLA patients who are eligible and interested in enrolling in the study will be invited to a consent appointment at the VA. At this point forward, all study activities will align with the approved protocols for the current VA study. These UCLA patients will be enrolled as non-Veterans. The informed consent process will be identical to the process described above, except on-Veteran participants will sign a separate consent form that includes a statement that an electronic VA medical record will be established for all non-Veteran participants. They will also sign the VA HIPAA, and VHA Form 10-0483, Acknowledgement of the Notice of Privacy Practices. Non-Veteran participants also will be asked to sign a UCLA HIPAA form, so [name] and other study staff who have a UCLA appointment, can access the UCLA electronic medical record.

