#### Randomization

Individuals who complete the baseline assessment and meet all inclusion/exclusion criteria will be randomly assigned to one of the two intervention groups: MTcap (N=66) or SGT+CBTI (N=66). Both interventions are described below. Randomization procedures will follow the CONSORT criteria for randomized trials. Stratified

randomization will be used to ensure that both groups are balanced in baseline hypnotic drug type half-life (i.e., temazepam/zolpidem; alprazolam/lorazepam; clonazepam) and gender. The study statistician will generate the stratified randomization sequence. A set of envelopes containing the group assignment will be generated and stored in a secure file drawer accessible only authorized staff. Once final eligibility is determined, the data manager will open the next envelope in sequence within the appropriate stratum.

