# Primary Analysis Plan

We plan to randomize 132 individuals, of whom we expect 13% to drop out (i.e., fail to complete assessments) by 6-months, yielding N=114 participants with complete data ( $\sim$  57 per group). We base this drop-out on our completed study ([name] VA Merit 08-295). We will include terms for stratification characteristics and covariates for baseline pain intensity, PHQ-9, and opioid use in all of the models. All analyses below assume  $\alpha$ =0.05, power=0.80, two-sided hypothesis tests, and intention-to-treat approach. Effect sizes are in the measure's natural units and Cohen's d (large=.8; medium=.5; small=.2).

- (H1a) Participants who receive MTcap will have increased likelihood of hypnotic discontinuation post-treatment and at 6 months follow-up compared with those who receive SGT+CBTI: Hypnotic discontinuation (yes=1/no=0) will be regressed on treatment group assignment (MTcap vs. SGT+CBTI) in two logistic regression models (post-treatment and 6 months follow-up). Sample size calculations establish that 114 participants will be adequate to detect a difference of 21% to 26% between the MTcap and SGT+CBTI groups, depending upon the discontinuation percentage of the SGT+CBTI group (59% to 63% at follow-up in prior studies). In our feasibility study, 100% discontinued hypnotics post-treatment. We will use multiple imputation.

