# Exploratory Analysis Plan (E1)

We will describe the frequency of falls in each arm. We will test whether MTcap is associated with not falling, using logistic regression (dependent variable [DV] is fall [binary]), which will be predicted as a function of treatment group assignment. E2: Mediation analyses to elucidate the relationship between insomnia severity, hypnotic use, and balance will be conducted using a statistical macro developed by UCLA, which simultaneously tests for the associations of the independent variable (IV; ISI) on the DV (balance), IV on the mediator (hypnotic dose in diazepam equivalents), and IV (ISI) plus mediator (hypnotic dose) on DV (balance) (Sobel, Goodman, and Goodman II tests). Similar mediation analyses (using a Stata user written command for binary mediation) will be performed for the DV, history of fall.

Amendment: We will conduct the same analyses above, but with the addition of data from participants recruited and seen at the UCLA Health site. These data will be transferred in a limited data set from UCLA Health to VA Greater Los Angeles under an approved data use agreement.

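### The pooled VA and UCLA analyses have no site term, UCLA-site randomisation is not described, and no data set is named primary

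*Combined protocol and SAP*

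**What the plan says.** The amendment paragraph closing the Exploratory Analysis Plan (E1) says the analyses above it will be repeated "with the addition of data from participants recruited and seen at the UCLA Health site". It adds that these data reach the VA as a limited data set under a data use agreement. It gives no UCLA sample size, randomisation method, site covariate or primary data set.

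The Primary Analysis Plan lists the adjustment terms for all models: the stratification characteristics, baseline pain intensity, PHQ-9 and opioid use. It assumes alpha "0.05, power=0.80, two-sided hypothesis tests" and intention to treat, and uses multiple imputation for H1a. Under Randomization, the strata keep the arms "balanced in baseline hypnotic drug type half-life" and in gender. Site is in neither list.

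The sample size is that of the original design: "We plan to randomize 132 individuals, of whom we expect 13% to drop out", "yielding N=114 participants with complete data". Whether UCLA participants fall inside the 132 or on top of it is not said.

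The Amendment to recruitment protocol describes a UCLA route in which patients are consented at the VA and enrolled as non-Veterans. It then says: "At this point forward, all study activities will align with the approved protocols for the current VA study". The Setting paragraph places all in-person assessments and treatment sessions within the VA system.

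**The concern.** UCLA patients come from another health system and may differ in prognosis, drop-out and response. Site is known at baseline and costs almost nothing to adjust for. Leaving it out has three possible consequences.

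- If the arms are unbalanced within site, or the allocation ratio differs by site, part of the site difference is read as a treatment effect in the logistic models.
- If the sites change differently over time, that difference enters the group-by-time contrasts.
- If drop-out and outcome both vary by site, an imputation model without site makes the missing-at-random assumption harder to defend.

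Separately, when no data set is named primary, the choice between VA-only and pooled results can be made after both are seen.

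**Working it through.** **Reproducing the plan's figures.** 132 × (1 − 0.13) = 114.8, which matches the stated 114 (57 per arm). The detectable post-test difference is (1.960 + 0.842) × √(2/57) = 0.525, against 0.52 stated for H4. Multiplying by √(2(1 − r)) for a change from baseline gives 0.306 (r = 0.83, H1b), 0.580 (r = 0.39, H2) and 0.498 (r = 0.55, H3), against 0.30, 0.58 and 0.50 stated. The power statements for H1b, H2 and H3 are thus change-from-baseline calculations, which matters for the mixed models below.

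**H1a, attenuation when site is omitted.** Assume 61% discontinuation on SGT+CBTI (midpoint of the plan's 59% to 63%) and 84% on MTcap (a 23-point gap, inside the plan's 21 to 26). The within-site log odds ratio is logit(0.84) − logit(0.61) = 1.211. Let w be the UCLA share and OR the site odds ratio, both assumed. The pooled rate in each arm is (1 − w)p + w·expit(logit p + ln OR).

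| w | OR | log OR without site | attenuation |
|---|---|---|---|
| 0.15 | 1.5 | 1.207 | 0.3% |
| 0.25 | 2 | 1.195 | 1.3% |
| 0.50 | 3 | 1.162 | 4.1% |

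**H1a, imbalance.** The unadjusted arm difference shifts by (UCLA share in MTcap − UCLA share in SGT+CBTI) × site difference. Assume 30 UCLA patients among 162, split 18 and 12, and a 20-point site difference. The shift is (18/81 − 12/81) × 0.20 = 0.015, or 1.5 points. With about 70% discontinuing overall (assumed), the standard error is √(2 × 0.7 × 0.3/81) = 0.072, so the shift is about 0.2 standard errors. An imbalance that arises by chance is not bias in expectation. A different allocation ratio by site would be, and the plan does not exclude one.

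**Mixed models (H1b, H2, H3, H4).** The plan's contrasts are group by change from baseline. A site shift that is constant over time is subtracted out. As a check, 172 simulated participants (40 from UCLA, r = 0.39) were given constant site shifts of 0, 0.5 and 1 SD. The standard error of the change contrast was 0.166, 0.172 and 0.168, with no trend. Only site differences in change remain, and a site main effect alone would not remove them.

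**Two data sets, if both can be claimed.** VA-only data are nested in the pooled data. With 1:1 allocation and equal variances, the two test statistics correlate at ρ = √(132/(132 + n)), where n is the assumed number of UCLA participants added. The chance that at least one exceeds 1.96 in absolute value under the null is:

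| n | ρ | false-positive chance |
|---|---|---|
| 10 | 0.964 | 6.2% |
| 20 | 0.932 | 6.7% |
| 40 | 0.876 | 7.3% |
| 66 | 0.816 | 7.7% |
| 132 | 0.707 | 8.3% |

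Two independent tests would give 1 − 0.95² = 9.75%. These figures are per test and do not count the plan's separate time points.

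**The case against.** A reader might infer that every hypothesis gets two chances at 0.05. The documents do not establish that. The amendment can equally mean that one pooled analysis replaces the VA-only one. Because it sits under the exploratory heading, it may reach only E1 and E2. Nothing says that both results will be claimed. What stands is the ambiguity: the text supports each of these readings, and on the narrowest one the falls model still has no site term.

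A reader might also infer that site differences generally inflate the error. For H1b and H2 to H4, a constant site shift cancels, and for H1a the attenuation is slight. This part of the objection stands.

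Nor do the documents show that randomisation at UCLA ignores site. The envelope procedure under Randomization is the VA one, and UCLA could have its own sequence. The gap is that its method is not described.

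Finally, the recruitment amendment and the analysis amendment need not contradict each other. Patients followed at the VA would not obviously need a data transfer from UCLA, so there may be two UCLA groups. In that case neither site nor the VA-only data set is defined until the plan says how patients enrolled through the VA route are coded.

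**Conclusion.** The point holds in limited form. As written, the pooled models omit a known baseline factor, UCLA-site randomisation and numbers are missing, and the scope and status of the pooled analysis are open. The likely numerical effect is small: 0.3% to 4.1% attenuation for H1a, a shift of about 1.5 points in the imbalance example against a design difference of 21 to 26 points, and 6% to 8% false positives per test only if both data sets are tested and either can be claimed. All of these rest on assumed UCLA numbers and site differences, because the documents give none. H1a and falls are where a site main effect matters most. The mixed models are exposed only to site differences in change. The documents do not settle which data set should be primary: the trial is framed around older Veterans and powered on 132 randomised, so VA-only is as defensible as pooled.

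**What to change.** - Define site, including how UCLA patients enrolled through the VA are coded, and reconcile the Setting paragraph, the Amendment to recruitment protocol and the analysis amendment on where UCLA participants are seen.
- State the UCLA sample size, whether it is inside or additional to the 132, and how those participants are randomised.
- Add site as a fixed effect to every pooled model, with site-by-time in the mixed models, and include site in the multiple-imputation model.
- Say whether the amendment covers H1 to H4 or only the exploratory analyses. Before unblinded analysis, name VA-only or pooled (the sponsor's choice) as primary for each hypothesis, and label the other a sensitivity analysis with no separate claim. The error then stays at 0.05 per test.

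The cost is a few sentences, about one degree of freedom in each logistic model, and up to three in a mixed model with three time points (one for site, two for site-by-time).
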